8.3. CONFIDENTIALITY	10
8.4. INDEMNITY	10
8.5. SPONSOR	11
8.6. FUNDING	11
8.7. AUDITS	11
9. STUDY MANAGEMENT	11
10. PUBLICATION POLICY	11
11. REFERENCES	11

GLOSSARY OF ABBREVIATIONS

KEYWORDS

Chronic venous disease
Chronic venous insufficiency
Venous leg ulcers
Diagnostics
Vascular Scientists
Delphi
Cost effectiveness

STUDY SUMMARY

TITLE Estimating & comparing the performance, clinical effectiveness, and cost-effectiveness of current diagnostic options for patients that present to primary care with suspected venous ulcers.

DESIGN Online questionnaire . survey study

AIMS The main objective of this project is to determine the role/position of diagnostic imaging in the patient journey for a patient with active or healed ulceration.

OUTCOME MEASURES To determine the minimum diagnostics that any patient that presents to primary care with a suspected venous ulcer should receive. Assess the cost effectiveness of implementing these established diagnostics into different care models.

POPULATION Primary care health professionals and vascular scientists.

ELIGIBILITY Primary care practitioners working in the UK and vascular scientists working in secondary care in the UK.

DURATION 20 months

1. INTRODUCTION

1.1. BACKGROUND

Chronic venous disease (CVD) encompasses a broad spectrum of venous abnormalities in which there is a significant compromise in the return of blood to the heart. CVD is both prevalent and progressive in nature (Ortega et al. 2021). CVD refers to complications that arise in the lower extremity due to retrograde (reverse) venous flow, also known as chronic venous insufficiency (CVI) which is caused by a persistent elevation in venous pressures, commonly referred to as venous hypertension (Millan et al. 2019). There are multiple potential causes of venous insufficiency and fundamentally venous hypertension. The clinical presentation of CVI can vary depending on the severity of the disease, with the most severe cases presenting with leg ulceration (Escudero Rodriguez et al. 2014). NICE define a venous leg ulcer (VLU) as a loss of skin that take more than 2 weeks to heal due to sustained venous hypertension (NICE 2021). Other definitions include a breach in the epithelial integrity of the skin occurring between the knee and malleoli (Poskitt and Gohel 2019). The typical location and most common presentation of VLUs is the medial gaiter area of the leg, however lateral and foot ulceration may also occur and be associated with venous insufficiency and or hypertension (Poskitt and Gohel 2019).

Leg ulcers contribute to a huge socio-economic impact on the NHS annually, with over an excess of 100,000 active leg ulcers in the UK at any one time (Cunliffe 2021). They have been documented to be a significant burden on healthcare systems internationally and particularly in association with primary and community care. In addition to the associated extreme cost burden, they are associated with detrimental effects on patients quality of life, causing pain, discomfort and overall distress to the patients (Alguire and Mathews 1997; Barwell et al. 2000).

Currently there is a wide variation in practice of leg ulcer management leading to a discrepancy in treatment that patients are receiving. Data collated from the Health Improvement Network database has shown that more than 90% ulcers remained unhealed at 6 months (Guest et al. 2012). This, alongside other supporting reviews, leads to questions of these alarmingly low healing rates (White et al. 2013). Evidence suggests that this cohort of patients are being managed sub optimally in primary care and a more standardized approach needs to be taken to improve overall ulcer healing rates and ulcer prevent recurrence. Dressings alone will not heal these ulcers and prevent recurrence, the underlying cause of these ulcers must be determined and this cause treated (Cunliffe 2021). Diagnostics play an important role in the management of venous leg ulceration with multiple literature sources emphasising the importance of diagnostic testing to confirm a diagnosis of venous insufficiency, to determine the aetiology, localise the anatomical site and level / source of disease (O'Donnell et al. 2014; DeMaeseneer et al. 2022). Duplex ultrasound is a non-invasive, cost effective and a reproducible imaging modality commonly used determine the source of venous insufficiency and to map the venous system (Alguire and Mathews 1997). It is believed that to perform the correct and necessary venous interventions procedures, a venous duplex ultrasound scan should be performed to delineate the source or reflux and all potential reflux targets (O'Donnell et al. 2014). To further support this, early endovenous ablation of superficial vein reflux has been shown to result in faster healing of

venous leg ulcers and a longer period of ulcer free time, compared to those that received delayed endovenous ablation (Gohel et al. 2019).

Primary care has limited resources for performing diagnostic investigations for suspected venous leg ulcers and limited appropriately trained staff to manage these patients.

Additionally, the pathway for onward referral to a specialist ulcer service are variable and vary by geographical location (NHS England 2018).

In the UK, currently the only diagnostic test mentioned in the NICE guidelines with regards to managing these patients is an ABPI. This test is to determine the state of a patients arterial blood supply and therefore the suitability of these patients to go into compression bandaging (NICE 2021). Patients presenting with leg ulcers are therefore receiving different diagnostic, management, and treatment pathways and most importantly, they are all receiving this care at different time intervals depending on where they present.

1.2. RATIONALE FOR CURRENT STUDY

The pathway of current practice from the patient first presenting to receiving this treatment, including vascular diagnostics, has not been investigated in detail, and is therefore not optimised. There is a lack of evidence and written documentation regarding diagnostics in the available guidelines. This means that there is a lack of standardised care for this cohort of patients across the UK.

It is hypothesised that by understanding how primary care currently refer onto specialist centres and establishing a consensus on what diagnostic tests should be performed on this cohort of patients, a conclusion on the most cost and clinical effective method of delivering diagnostics and care to this cohort of patients can be established. It is hypothesised that this will involve generating clearer guidelines and standardised pathways based on up-to-date literature for when VLU patients initially present into primary care, including when they should be referred onto specialist vascular centres, what specific diagnostic tests should be performed upon initial presentation and an outline of treatment options. The most cost-effective method may also suggest the initiation of specialist leg ulcer clinics involving a multidisciplinary team.

2. STUDY OBJECTIVES

The aim of this project is to determine the minimum diagnostics that any patient that presents to primary care with a suspected venous ulcer should receive and look at the most effective way to implement this.

Primary Objective

- 1) To determine the role/position of diagnostic imaging in the patient journey for a patient with active or healed ulceration.

Secondary Objective

- 1) To determine the current practice in primary care for venous ulcer management.
- 2) To determine the current practice for diagnosis and management of suspected venous leg ulcers in vascular scientist departments across the UK
- 3) To establish what the minimum diagnostics should be for this cohort of patients including what scans should be performed and can a set criterion be applied to this cohort of patients.
- 4) To determine the cost effectiveness of implementing this in both primary and secondary care settings.

3. STUDY DESIGN

- 1) To determine the current practice of primary care, a questionnaire will be designed using Qualtrics management platform (Qualtrics, UT, USA) to assess various aspects of the national management and diagnostics for venous leg ulceration. A similar methodology will be utilised to that of a previous primary care questionnaire that was disseminated to primary care practitioners pre and post the EVRA trial (Heatley et al. 2020). Key areas to be investigated will be whether there are one main set of guidelines that primary care practitioners follow, the availability of services they have in their centre and if they have any major barriers to onward referrals. The questionnaire is attached, it has been tested and optimised after engagement with key stakeholders.
- 2) To determine the current diagnostic pathways for this cohort of patients in vascular departments across the UK and to try and establish a uniform standardised diagnostic pathway, a Delphi consensus will be performed amongst vascular scientists. Responses will be summarised between each round and fed back to the participants. This will be used to determine a consensus on the best and most realistic diagnostic management of these patients. For the purpose of this study, a consensus has been defined at a $\geq 70\%$ agreement. The hope is that by involving those that could be directly implicated by any changes to the guidelines, it will initiate interest and engagement both during the consensus itself and implementing the findings of the consensus. The first round of the Delphi questionnaire is attached, it has been tested and optimised after engagement with key stakeholders.
- 3) To investigate whether there is a minimum diagnostic that can be recommended for this cohort of patients the current literature regarding typical pattern of reflux and anatomical location of ulcers will be reviewed. This may involve details on who should perform and where these investigations should or could be performed. To determine whether there is a minimum number of diagnostic investigations that needs to be carried for these patients, in conjunction with the results from the Delphi consensus, a detailed literature review will be carried out looking into the location of venous ulcer and source of reflux. This will be done by initially identifying PICOS criteria. I will then develop a search strategy and input this into Ovid. From the papers identified in this search, I will perform abstract screening against the pre-defined PICOS criteria, complete full text screening, data and information extraction, analysis, and synthesis. This is to determine whether all patients require a full venous

duplex scan, or whether in some situations, a quicker less detailed 'spot check' scan can be performed. This in turn will also contribute valuable information regarding the setting for the diagnostic testing.

- 4) To establish the cost effectiveness of different proposed models, a Markov model will be constructed to estimate the health outcomes and costs over 5 years of different testing strategies applied to a cohort of VLU patients. Variations of diagnostic tests combinations and settings to be investigated may include, ABPI in primary care and full venous duplex in secondary care, ABPI and venous duplex in primary care, ABPI and venous duplex in secondary care. Health outcomes will be venous ulcer healing rates and venous ulcer recurrence rates. Sensitivity analyse will also be performed (Normahani et al. 2021; Epstein et al. 2018).

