6. STATISTICS AND DATA ANALYSIS

A series of descriptive statistics will be carried out on the results obtained from the questionnaire and consensus. Advice will be sought from [name], The University of Edinburgh.

Data and all appropriate documentation will be stored for a minimum of 10 years after the completion of the study

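### The Markov model is given two separate health outcomes, healing and recurrence, and no single effect measure by which to rank strategies on cost-effectiveness

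*Protocol*

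**What the plan says.** Protocol Section 3, item 4 says that "a Markov model will be constructed to estimate the health outcomes and costs over 5 years", comparing several combinations of test and care setting. It then names the effects: "Health outcomes will be venous ulcer healing rates and venous ulcer recurrence rates". A sentence on sensitivity analysis follows, with two economic studies cited.

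Elsewhere the protocol commits to a cost-effectiveness result:

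- Study Summary, outcome measures: "Assess the cost effectiveness of implementing these established diagnostics into different care models".
- Section 2, secondary objective 4: "To determine the cost effectiveness of implementing this in both primary and secondary care settings".
- Section 1.2: the project is expected to reach "a conclusion on the most cost and clinical effective method", and "The most cost-effective method may also suggest the initiation of specialist leg ulcer clinics involving a multidisciplinary team".

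Section 6 does not mention the model: "A series of descriptive statistics will be carried out on the results obtained from the questionnaire and consensus". Section 3.1 likewise covers only the questionnaire and the Delphi.

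**The concern.** A cost-effectiveness ranking needs one effect scale. With two, every pair of strategies has two incremental ratios, and the protocol says neither which one decides nor how to combine them. If they disagree, an analyst who follows the protocol exactly either cannot rank the strategies or picks the measure once the results are known. In the second case the choice of measure determines the recommendation. Section 1.2 links that recommendation to the possible setting up of specialist clinics, so it could influence how services are organised.

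The two outcomes are also linked. Only a healed ulcer can recur, so a strategy that heals more ulcers can produce more recurrences even when the risk after healing is unchanged. A recurrence outcome without a stated denominator could count against it.

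**Working it through.** The protocol gives no ratio, threshold or model result, so there is no figure to reproduce. Two checks apply.

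**1. Is a combined measure given anywhere in the protocol?** Section 3 item 4 names two rates. Sections 3.1 and 6 do not deal with the model. Quality of life and ulcer-free time appear in Section 1.1 only as background. No section shown names QALYs, utilities, an incremental ratio, net benefit or a threshold, or says which rate takes precedence.

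**2. Can the two outcomes disagree when neither strategy worsens either one?**

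Model: two states (open, healed), 60 monthly cycles, all patients start open, no deaths. With monthly healing probability h and monthly recurrence probability r, the healed proportion H follows

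H(t+1) = H(t)(1 − r) + (1 − H(t))h.

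Ulcer-free months are the sum of [H(t) + H(t+1)]/2 over the 60 cycles.

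Inputs:

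- *Base healing, from the protocol.* Section 1.1 reports that "more than 90% ulcers remained unhealed at 6 months". At a constant rate the most this allows is h = 1 − 0.9^(1/6) = 0.0174 per month.
- *Base recurrence, assumed:* r = 0.01, 0.02 or 0.03 per month.
- *Strategy A, assumed:* healing 1.1h, recurrence r.
- *Strategy B, assumed:* healing h, recurrence 0.75r.
- *Cost, assumed:* equal for A and B.

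Ever healed within 5 years, 1 − (1 − h)^60:

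- Comparator and B: 1 − (1 − 0.0174)^60 = 65.1%.
- A: 1 − (1 − 1.1 × 0.0174)^60 = 68.7%.

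Healing therefore prefers A.

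Recurrences per 100 ulcer-free person-years at r = 0.02:

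- Comparator and A: 23.7.
- B: 17.8.

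Recurrence therefore prefers B. If recurrences are counted per 100 patients instead, A has 36.0 and the comparator 33.5, although A's recurrence probability is unchanged.

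Ulcer-free months over 5 years:

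| r per month | Comparator | Gain, A | Gain, B | Preferred |
|---|---|---|---|---|
| 0.01 | 19.57 | 1.41 | 0.76 | A |
| 0.02 | 16.95 | 1.26 | 1.23 | A, narrowly |
| 0.03 | 14.88 | 1.14 | 1.51 | B |

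The gains are equal at r = 0.0207. With assumed base healing of 4% or 8% per month, both above the bound from Section 1.1, they are equal at r = 0.0175 or 0.0141. Counting time at the start or end of each cycle changes the gains by at most 0.03 months and leaves the order the same at all three values of r.

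So healing alone always picks A and recurrence alone always picks B. The combined measure picks one or the other according to the size of the base recurrence rate, a trade-off that neither rate shows by itself.

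**The case against.** The strongest objection is that this is model detail commonly left to an analysis plan, which is not at hand. Section 3 item 4 is only an outline, and an open/healed model already yields ulcer-free time, so what is missing is a name. Part of this stands: the remedy is small and can be made at any time before the model is run. But the protocol does not leave the outcomes open. It states what they will be, and that choice is the point at issue.

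Costs may also be set beside several clinical outcomes without a single ratio, and the wording about a most cost-effective method comes only from the hedged rationale in Section 1.2. Secondary objective 4 promises no single winner. That is fair, but a list of costs and consequences would not deliver the conclusion that Section 1.2 expects.

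The illustration is artificial. A changes only healing, B changes only recurrence, and costs are equal. The planned strategies share tests, and Section 1.1 reports that early ablation gave both faster healing and more ulcer-free time, so the outcomes may well move together. One strategy could also be better on everything. These points make disagreement less likely, but the plan cannot count on them.

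Finally, the two cited economic studies might use a combined measure. Their content is not at hand, and the protocol does not say that it adopts an effect measure from them.

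**Conclusion.** The point holds. The protocol names two health outcomes, gives no rule for combining or ordering them, and expects a cost-effectiveness conclusion that they cannot supply when they disagree. The illustration shows that they can disagree even when neither strategy makes either outcome worse. It does not show that they will, or how likely that is. Only the base healing bound comes from the protocol; the recurrence rates, effect sizes and equal costs are assumptions. This is a worthwhile, inexpensive improvement to a secondary objective, with no bearing on the survey or the Delphi.

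**What to change.** In Section 3 item 4, name one main effect measure that combines healing and recurrence over the 5 years, before the model is run. Either of these would do:

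- **Ulcer-free time**, which comes from the model's own states and needs no further inputs.
- **QALYs**, which need published utilities for the open and healed states, varied in the sensitivity analysis already planned.

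In a plain two-state model, QALYs gained = (utility healed − utility open) × ulcer-free years gained, so both measures put the strategies in the same order on effect.

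Report incremental cost per unit of the chosen measure, or net benefit. Keep healing and recurrence as descriptive outputs, with recurrence expressed per ulcer-free person-time.

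The cost is two sentences and slightly more analysis, with no new data collection. If QALYs are chosen, the result will depend on external utilities that the protocol does not give.

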3.1. STUDY OUTCOME MEASURES

- 1) The electronic questionnaire to primary care networks will be shared via various social media platforms and will remain open for 1 months for responses. The questionnaire will be reposted at regular intervals to promote engagement.
- 2) The Delphi consensus will continue until a consensus has been reached, $\geq 70\%$ agreement. Each round of the consensus will be open for one month. Response analysis and design and dissemination of the next round will occur within two weeks.

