5. ASSESSMENT AND FOLLOW-UP

There will be no formal assessment or follow-up in this study.

Definition of end of study:

The study will end when the primary care questionnaire has been live for one month and when a consensus has been reached amongst vascular scientists, defined as a >70% agreement.

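### As written, the Delphi, and with it the study, can close only once agreement is reached; the protocol text shown sets no maximum number of rounds and no way to close and report without consensus

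*Protocol*

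**What the plan says.** Four places in the protocol bear on how the Delphi ends.

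- **Section 3, item 2.** One purpose of the Delphi is "to try and establish a uniform standardised diagnostic pathway". The threshold in this section is 70% or more (≥70%). Panel members see a summary of the answers after every round.
- **Section 3.1, item 2.** The continuation rule is "The Delphi consensus will continue until a consensus has been reached", and the threshold is again ≥70%. A round lasts one month, and up to two weeks are then allowed for analysing the answers and sending out the following one.
- **Section 5, definition of end of study.** The wording is "The study will end when the primary care questionnaire has been live for one month and when a consensus has been reached". In this section the threshold is strictly more than 70% (>70%).
- **Study summary.** The project lasts 20 months.

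Section 6 plans descriptive statistics for both the questionnaire and the consensus exercise. Section 4.4 covers withdrawal of individual participants, which does not end the process. No section shown gives a maximum number of rounds, a stop for stable disagreement, or a rule for closing an item below the threshold.

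**The concern.** The decision to stop depends on the result, and only one result permits stopping. Section 3 allows that a uniform pathway may not be achieved, yet Sections 3.1 and 5 give that case no ending: if the threshold is not met, the only stated step is another round.

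Section 3, item 3 uses the Delphi result, together with a literature review, to decide the minimum investigations, which is secondary objective 3. Persistent disagreement about a test would be a relevant answer to that objective. If the plan does not recognise it as an end point, the investigators must either keep going or depart from the protocol after seeing the responses. In the second case, the choice of when to stop and what to call the result is made with the data in view.

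**Working it through.** The protocol states no number of rounds, panel size or probability for the Delphi, so there is no figure of its own to reproduce. The check is a reading of the rules side by side, followed by two short calculations.

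**1. Is consensus necessary for closure?** Section 3.1 ties the end of the rounds to consensus. Section 5 joins two conditions, the questionnaire period and consensus, so both must hold before the study ends. Neither section offers an alternative. Consensus is therefore necessary, on the text, both for the Delphi to close and for the study to end.

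**2. Does the 20-month duration act as a cap?** Inputs from Section 3.1: each round is open for 1 month, with up to two weeks (taken as 0.5 month) before the next. For k rounds the time needed is at most

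k × 1 + (k − 1) × 0.5 = 1.5k − 0.5 months.

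| Rounds | Time, up to |
|---|---|
| 2 | 2.5 months |
| 3 | 4.0 months |
| 4 | 5.5 months |
| 13 | 19.0 months |
| 14 | 20.5 months |

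So 13 rounds fit within 20 months if the whole project period went to the Delphi. If two weeks is counted as 0.46 month, 14 rounds just fit: 14 + 13 × 0.46 = 19.98. Either way the limit is too loose to be a practical stopping rule. The duration is also given for the project as a whole. If consensus had not come by month 20, the Study summary and Section 5 would conflict, and no text says which prevails or what is reported.

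**3. Direction of the effect.** Suppose a question is put again, in some form, after feedback. The chance that it has met the threshold in at least one round cannot fall as more rounds are allowed, because a single success is enough. This holds whether or not rounds are independent. With no cap and no other exit, the rule leans towards a declaration of consensus. The size of the effect depends on panel size, true agreement and how far respondents move after feedback. The protocol gives none of these.

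**4. The two threshold signs.** The smallest number agreeing that satisfies ≥70% of n respondents is 0.7n rounded up. For >70% it is 0.7n rounded down, plus 1. These differ only when 0.7n is a whole number, that is, when n is divisible by 10. For example, 21 of 30 meets the rule in Sections 3 and 3.1 but not the one in Section 5.

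**The case against.** The strongest case on the other side has five parts.

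- **Disagreement would still be visible.** A reader might infer that the study cannot show that vascular scientists disagree. The documents do not support that: Section 3 has responses summarised after each round, and Section 6 plans descriptive statistics, so low percentages would be produced and could be published. The purpose of describing current practice in vascular departments (secondary objective 2) is met with or without consensus. This part stands. What is missing is a rule that lets the Delphi close on such a result.
- **The process is not literally endless.** A 20-month duration is stated, so a claim that there is no limit of any kind would go too far. It is nevertheless a loose ceiling, not tied to the Delphi.
- **Convergence through feedback is what a Delphi is for.** True, and later rounds may be redesigned rather than repeated. Feedback is not the fault; making success the only exit is. It is tempting to attach a probability by treating rounds as independent trials, but the same panel answers after seeing summaries and its size is not given, so no such figure would be sound.
- **A cap may be stated elsewhere.** The attached first-round questionnaire and the participant information sheet are not shown, nor is every section of the protocol. The point is therefore limited to the text shown, which refers to no cap.
- **This is detail for an analysis plan.** It would be, had the protocol been silent. The protocol fixes the stopping rule and the end of study itself, and an analysis plan that added a cap would contradict Sections 3.1 and 5.

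**Conclusion.** The concern holds. Sections 3.1 and 5 make reaching the threshold the only stated way for the Delphi, and so the study, to close, and the text shown has neither a maximum number of rounds nor a rule for closing and reporting below the threshold. The direction of the effect, towards declaring consensus, follows from the rule; its size cannot be derived from the protocol. The conclusion rests on the wording and on no assumed panel.

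It should be fixed, but in proportion: this is an online survey of professionals with descriptive analysis, and the objective most affected is a secondary one that also draws on a literature review. The difference between ≥70% and >70% is minor, since it matters only at exactly 70%, and the plain sign in Section 5 might be an artefact of how the text was read from the PDF. A reader should not take it to mean that two materially different definitions of consensus are in use.

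**What to change.** Amend Sections 3, 3.1 and 5 before round 1:

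1. State a maximum number of rounds. Three is an illustration only; it would take up to 4.0 of the 20 months (20%).
2. State what the threshold applies to. The natural reading is each item, among that round's respondents, but the protocol does not say so. If another unit or denominator is intended, name it. Without this the end rule in step 4 cannot be applied.
3. Report whatever remains below the threshold after the last round as no consensus, with its agreement percentage, as a valid result.
4. Define the end of the Delphi, and its part of the end of study, as the close of the last permitted round, or earlier if every unit defined in step 2 has met the threshold.
5. Use one threshold sign throughout, either ≥70% or >70%.

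The cost is protocol wording only. The downside is that some items may end as no consensus, so the Delphi may not deliver a complete standardised pathway.
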